6.3.5. Imputation of Missing Data for Evaluation of Efficacy

Guidelines regarding how missing data will be handled for each efficacy endpoint are described below.

6.3.5.1. Hemoglobin Responder

- If Hb assessment is missed at both Week 20 and Week 24 due to dropout, VOC, or VOC hospitalization: Subject will be treated as a non-responder. If Hb at one of the two time points is non-missing, Hb response assessment will be based on the non-missing Hb value.
- Initiation of HU post randomization and prior to Week 24: Subject will be treated as a non-responder.

[figure not shown]
- RBC transfusions: A participant who receives a transfusion due to anemia within 8 weeks (12 weeks for sensitivity analysis) of the Week 24 Hb assessment will be deemed a non-responder. For subjects receiving transfusion due to reasons other than anemia within 8 weeks (12 weeks for sensitivity analysis) of the Week 24 Hb assessment, Week 24 Hb will be imputed with the last Hb assessment prior to the transfusion.

Example: In Figure 1, an RBC transfusion due to anemia occurred at Day 114. If the Week 24 Hb assessment occurs before Day 170 then the participant will be deemed a non-responder; otherwise the Week 24 Hb measure will then be compared to Baseline to determine whether the participant meets the definition of responder (i.e. $8.1 - 7.95 = 0.15$, which is classified as a non-responder). If the RBC transfusion is not due to anemia, then the Hb assessment prior to Day 114 (i.e., the Week 12 assessment, which is 7.0 g/dL) will be used for imputation of Hb for assessments occurring from Study Day 114 to Study Day 170 (8-week imputation) or to Study Day 198 (12-week imputation). The Week 24 Hb measure will then be compared to Baseline to determine whether the participant meets the definition of responder.

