Hemoglobin (Hb) response is based on the difference between the average value of Hb levels at Week 20 (Hb20) and Week 24 (Hb24) and baseline Hb level (HbB). A subject is considered to be a Hb responder if $[\text{mean}(\text{Hb20}, \text{Hb24}) - \text{HbB}] > 1 \text{ g/dL}$. If Hb20 or Hb24 is missing, then the calculation will use the non-missing Hb level. Regardless of calculated difference, subjects will be classified as a non-responder if any of the non-responder criteria in [Section 6.3.5.1](#) are met.

Hemoglobin Worsening at Week 24

- Severe anemic episode - worst Hb between weeks 12 and 24 inclusive is $< 5.5 \text{ g/dL}$
- Acute anemic episode - worst Hb between weeks 12 and 24 inclusive, is $\geq 5.5 \text{ g/dL}$ and $< 7 \text{ g/dL}$

Rate of Opioid Use During Treatment Period

The rate of opioid use is calculated as the number of days opioids were taken for SCD symptom management (as recorded in the eDiary) divided by the number of days with non-missing eDiary data from date of randomization to date of last dose.

Total Symptom Score (TSS)

For each subject, the TSS will be computed as follows: The Baseline TSS is the average of the scores during the 28 to 35-day Screening period. Similarly, post randomization when there is at least 75% compliance during a 4-week period, the TSS is the average score for each 4-week period. The 4-week periods are Weeks 1-4 (Study Day 1-28), Weeks 5-8 (Study Day 29-56), and Weeks 9-12 (Study Day 57-84) and follows similarly for subjects whose involvement exceeds 12 weeks up to Week 24. If there is a delay in initiating study treatment, all TSS data prior to administering treatment will be included with the Screening period data. All TSS data post dose through Study Day 28 will constitute Weeks 1-4. If missing data in a 4-week period is due to lack of compliance or subject dropout, the TSS will be set to missing for the 4-week period. Missing data due to VOC, VOC hospitalization or RBC transfusion will be imputed as described

in Section 6.3.5. Compliance of at least 60% during each 4-week period will also be examined in a sensitivity analysis for TSS.

TSS₁₀₀ is TSS rescaled from a 27-point scale to 100-point scale. Algebraically, this is accomplished as follows:

$$TSS_{100} = TSS \times \frac{100}{27}.$$

Clinical Global Impression of Change

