8.2. Efficacy Analysis

8.2.1. Primary Endpoint

8.2.1.1. Primary Analysis of Hemoglobin Response

For the primary analysis of Hb response, individual subject data through Week 24 will be included.

The Hb response rate will be analyzed using an exact Cochran-Mantel-Haenszel (CMH) general association test with imputation rules outlined in [Section 6.3.5](#). Each voxelotor dose group (900 mg and 1500 mg) will be compared to placebo while stratifying for the randomization stratification factor of HU use, age group and geographic region. Sample SAS code for the exact CMH general association test will be similar to the following:

```
PROC LOGISTIC;  
  CLASS treatment/PARAM=REF;  
  FREQ count;  
  MODEL response = treatment;  
  STRATA stratum;  
  EXACT treatment;  
RUN;
```

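### The transfusion rules for Hb response are dated only from the Week 24 Hb, but response averages Weeks 20 and 24, so a post-transfusion Week 20 Hb can enter the primary endpoint

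*SAP*

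**What the plan says.** **Endpoint.** SAP Section 4 makes response "based on the difference between the average value of Hb levels at Week 20 (Hb20) and Week 24 (Hb24) and baseline Hb level", with a threshold of more than 1 g/dL. It adds: "If Hb20 or Hb24 is missing, then the calculation will use the non-missing Hb level". The non-responder criteria of SAP 6.3.5.1 override the calculated difference.

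**Anemia transfusions.** Under SAP 6.3.5.1, a participant transfused for anemia "within 8 weeks (12 weeks for sensitivity analysis) of the Week 24 Hb assessment will be deemed a non-responder".

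**Other transfusions.** With the same look-back from Week 24, "Week 24 Hb will be imputed with the last Hb assessment prior to the transfusion".

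**Worked example (transfusion on Day 114).** The anemia case reads: "If the Week 24 Hb assessment occurs before Day 170 then the participant will be deemed a non-responder". For a later assessment, the example tests the Week 24 value on its own against baseline; the figures shown are 8.1 - 7.95 = 0.15. In the non-anemia case, the Week 12 value of 7.0 g/dL "will be used for imputation of Hb for assessments occurring from Study Day 114 to Study Day 170" (Day 198 for the 12-week version).

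**Use in the primary test.** Under SAP 8.2.1.1, the response rate is "analyzed using an exact Cochran-Mantel-Haenszel (CMH) general association test with imputation rules outlined in" Section 6.3.5. These sentences therefore decide who is a responder in the primary analysis.

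**Protocol.** Protocol 8.4.2.1 dates the anemia rule from the endpoint visit, which Protocol 4.14.2.2 sets at Week 24 for Groups 2 and 3.

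**The concern.** The plan means to stop Hb measured within 8 weeks after a transfusion from counting as drug response. The endpoint rests on two Hb values, but the rule protects only one of them. The Week 20 value carries half the weight, and all of it when Week 24 is missing.

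The non-anemia sentence and its example also differ on whether the Week 20 Hb is replaced. Two programmers working from the same page could classify the same participant differently. What is at stake is a single, reproducible derivation of the primary endpoint.

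**Working it through.** **Inputs.** Target days are 140 (Week 20) and 168 (Week 24). The protocol ranges are Days 135-145 and 163-173, and the analysis windows are Days 127-154 and 155-210 (SAP Table 1). The look-backs are 8 weeks = 56 days and 12 weeks = 84 days. The example uses baseline 7.95, Week 24 Hb 8.1 and pre-transfusion Hb 7.0 (SAP 6.3.5.1). The planning rates are 10% on placebo and a 30-point difference, with about 90 per arm and alpha 0.0481 (SAP 6.1).

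**1. The plan's own figures reproduce.** 114 + 56 = 170; 114 + 84 = 198; 8.1 - 7.95 = 0.15.

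**2. Gap in the anemia rule.** A transfusion on day d escapes, yet is within 8 weeks of the Week 20 Hb, when 0 ≤ W20 - d ≤ 56 and W24 - d > 56. The number of such days is W24 - W20, capped at 57.

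| Visit days | Gap | Part also missed by the 12-week analysis |
|---|---|---|
| Target (140, 168) | Days 84-111, 28 days | 0 days |
| Protocol ranges | 18 (145, 163) to 38 (135, 173) days | 0-10 days |
| Table 1 windows | 1-57 days | 0-55 days |

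At target visits the Week 20 Hb then falls 140 - 111 = 29 to 140 - 84 = 56 days after transfusion.

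**3. What it takes to make a false responder.** The two changes from baseline must average more than 1 g/dL. If Week 24 is back at baseline, Week 20 must be more than 2 g/dL above it; if Week 24 is +0.5, more than 1.5. If Week 20 stands alone, more than 1.

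**4. The example participant, anemia case.** With a Week 24 Hb after Day 170, this participant is in the gap: a Week 20 Hb on Day 140 is 140 - 114 = 26 days after transfusion. Section 4 gives a responder if (Hb20 + 8.1)/2 - 7.95 > 1, that is, Hb20 > 9.80 g/dL. The example compares 8.1 alone with baseline.

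**5. The example participant, non-anemia case, Week 24 by Day 170.**
- The sentence replaces Week 24 only: (Hb20 + 7.0)/2 - 7.95 > 1 if Hb20 > 10.9 g/dL.
- The example's day range replaces both: 7.0 - 7.95 = -0.95, a non-responder whatever Hb20 was observed.

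**6. Day 170.** It is exactly 56 days after Day 114, so it is inside 8 weeks in the rule. The anemia example leaves it out, while the non-anemia range runs up to it.

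**7. Effect on the primary comparison.** Expected responders are 0.40 × 90 = 36 and 0.10 × 90 = 9. Fisher's two-sided test, used for planning, stands in here for the stratified exact test:
- 36 vs 22 (13 false placebo responders): p = 0.038, still below 0.0481.
- 36 vs 23 (14 false placebo responders): p = 0.056.
- The same number added to both arms, from 0 to 45: p never exceeds 0.0001.

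**The case against.** **The example settles the non-anemia part.** This largely stands. Days 114-170 contain the whole Week 20 analysis window, so the likely intent is to replace every Hb in the period. The sentence should follow the example. That does not help when the transfusion is more than 8 weeks before the Week 24 Hb, because the sentence is then not triggered.

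**Week 24 is a deliberate anchor, shared with the protocol.** It is consistent between the documents, so adding a Week 20 look-back is more than a correction of wording. But the anchor does not match an endpoint that averages two visits. The general rule in Protocol 8.4.2 and the per-assessment rule for hemolysis measures in SAP 6.3.5.2 do not amend the responder sentences or close the anemia gap.

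**The 12-week sensitivity analysis covers it.** At target visits it does, fully. Over the protocol ranges it can miss up to 10 gap days, and it leaves the primary derivation unchanged.

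**Some of the text cannot be seen.** This stands. Figure 1 is not visible, nor is the SAP text after Section 11, where the contents list programming specifications. A reader might infer that the plan has no anchor when Week 24 is missing, or that 8.1 - 7.95 is a mistake. Only the visible text can be said to lack an anchor. The 0.15 agrees with Section 4 if the Week 20 Hb is missing or also 8.1.

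**Divergent programming would surface.** SAP Section 8 requires independent programming, which would probably expose a difference. It would not say which derivation was pre-specified.

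**Conclusion.** The mismatch is real on the visible text and should be fixed. Followed as written, the anemia rule lets a post-transfusion Week 20 Hb into the primary endpoint for transfusions on Days 84-111 at target visits (18-38 days over the protocol ranges). The non-anemia sentence is narrower than its example, and Day 170 is treated inconsistently.

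A reader might infer that the 1500 mg result is in doubt. The documents do not support that. They give no transfusion rates by arm, so neither the number affected nor the direction of bias can be computed. At the planning rates it would take 14 false responders, all on placebo. The 57-day extreme over the analysis windows also overstates the usual case: the window's last day, Day 210, is 37 days past the end of the protocol range (210 - 173).

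The size rests on about 90 per arm, the planned response rates and an unstratified Fisher test. The finding is an ambiguous primary derivation with a likely small effect.

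**What to change.** In SAP 6.3.5.1, before Group 2b is unblinded and as an analysis rule only:

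1. Apply the 8-week rule (12-week for sensitivity) to each visit Hb that enters the response calculation. A transfusion for anemia within that time before the Week 20 or Week 24 Hb that is used makes the participant a non-responder. If Week 24 is missing, the look-back then runs from the Week 20 Hb.
2. For other transfusions, replace any Week 20 or Week 24 Hb from the transfusion date to 8 (12) weeks after with the last pre-transfusion Hb, before taking the mean.
3. Treat Day 170 the same way in the rule and the example. Restate the example with the Section 4 mean, consistent with Figure 1. In the non-anemia case with a Week 24 Hb of 8.1 after Day 170, it becomes (7.0 + 8.1)/2 - 7.95 = -0.40.
4. Report the response rate under the Week 24-only rule and the both-visits rule, with reclassifications by arm and by cohort (Groups 1 and 2a, n = 156; Group 2b, n = 118). Name the primary rule before unblinding.

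Two further steps are not needed: a fixed calendar anchor at Day 168 when Week 24 is missing, and a look-back from every value averaged within a window that runs to Day 210. Both would be new rules without support in the visible text.

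**Cost.** SAP wording, one example and one derivation; no new data. An unknown number of participants become non-responders, because at target visits the anemia look-back widens from Days 112-168 (57 days) to Days 84-168 (85 days). The integrity cost is that Sponsor Biostatistics was already unblinded to 156 of 274 participants (57%; SAP Sections 2 and 6.2). Reporting both rules by cohort makes any effect of the change visible.

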6.3.5.2. Hemolysis Measures Change from Baseline and hemolysis reduction

- Missing data due to subject dropout: For the primary method of analysis of this endpoint (mixed effect model for repeated measures [MMRM]), missing at random (MAR) will be assumed and no imputation will occur.
- Subjects initiating HU post randomization will be discontinued from the study. As such, only assessments prior to HU initiation will be used in this analysis.
- Missing Week 24 hemolysis data due to VOC or VOC hospitalization: For the primary method of analysis of hemolysis measures (MMRM), missing at random (MAR) will be assumed and no imputation will occur. For sensitivity analysis, the imputation rule for missed assessments due to VOC or VOC hospitalization will be assigned the hemolysis measurement from the last assessment (Table 1) occurring prior to commencement of VOC or hospitalization for VOC (including Screening and Day 1).
- RBC transfusions: Regardless of whether data are missing, post transfusion hemolysis lab results will be imputed by assigning the hemolysis measurement of the last assessment prior to transfusion (including Screening and Day 1). All hemolysis lab results starting on the transfusion date and ending 8 weeks after are imputed for the MMRM analysis of hemolysis measures and the assessment of hemolysis reduction at Week 24. All hemolysis lab results starting on the transfusion date and ending 12 weeks after are imputed for the related sensitivity analysis. See Figure 1. The imputation for Hb is similarly applied to all measures of hemolysis for the change from baseline analyses.

Figure 1: RBC Transfusion Imputation for Hb Assessment

6.3.5.3. Total Symptom Score (PRO measure)

- Missing data due to missed diary entries or subject dropout: If a subject has 7 or more missed diary entries unrelated to VOC or hospitalization due to VOC in a 4-week period, the TSS will be set to missing for that period. Specifically, determine the rate of compliance for each 4-week interval. If a 4-week interval has a compliance rate of less than 75% (or < 60% sensitivity), then the interval summary value is set to missing. Otherwise, the mean of the observations within the interval is used as the summary value.
- Subjects initiating HU post randomization will be discontinued from the study. As such, only assessments prior to HU initiation will be used in this analysis.
- Missing data due to VOC or VOC hospitalization: Subject will be assigned his/her worst TSS score prior to the commencement of the VOC or VOC hospitalization. Example: Assume a subject was hospitalized from Day 35 – Day 39 and did not respond to the SCDSM questionnaire during this period. For Days 35 – 39, the worst TSS score for the subject up to Day 35 will be used for each day PRO data are missing.
- RBC transfusions: Regardless of whether data are missing, post transfusion data will be imputed for the 8-week period (12-week period for sensitivity analysis) after the transfusion. The TSS in the last 4-week period with a non-missing score prior to transfusion (including the Screening period) will be substituted for each day during this 8-week period post transfusion (12-week period for sensitivity analysis). Specifically, determine the TSS for the last 4-week interval prior to transfusion which meets the compliance threshold. Use this value to impute 8 weeks (or 12 weeks for sensitivity analysis) post transfusion.

The PRO imputation rules have a hierarchy in situations where there are missing data and RBC transfusions have been administered during participation in the study. The ordering of imputation rules is as follows:

1. Impute missing TSS data due to VOC and/or VOC hospitalization as specified above.
2. Apply imputation rule based on rate of compliance for each 4-week interval as specified above.
3. Impute TSS data potentially affected by RBC transfusion as specified above.
4. Apply imputation rule based on rate of compliance once more for each 4-week interval as specified above.

If a subject no longer wishes to participate in the study and withdraws consent or if a subject initiates HU post randomization (resulting in discontinuation from the study), the end of study date is the last day in which imputation may occur, i.e. imputation will not surpass the end of study day.

Refer to Section 6.3.6 for details of imputing missing dates. Unless otherwise specified, no other missing data imputation is planned.

Example: For a given subject, assume an RBC transfusion occurs on Study Day 35. The largest TSS from the Screening Period (30 days) and Weeks 1-4 (28 days) will be used to impute the TSS on Day 35 through Day 91 (8 weeks). Based upon Figure 2, the Screening Period had an average TSS of 17 and Weeks 1-4 had 21.

Assume the average TSS prior to RBC transfusion for Days 29 -34 was 20. The average TSS for Weeks 5-8 is computed as follows:

$$\frac{[(34 - 29 + 1)20 + (56 - 35 + 1)21]}{(56 - 29 + 1)} = 20.79$$

The average TSS for Weeks 9-12 is 21.

After transfusion, on Days 91-112, assume the average TSS was 12. The average TSS for Weeks 13-16 is computed as follows:

$$\frac{[(91 - 85 + 1)21 + (112 - 92 + 1)12]}{(112 - 85 + 1)} = 14.25$$

Figure 2: RBC Transfusion Imputation for TSS Score

6.3.6. Imputation of Incomplete Dates

An incomplete date is any date for which either the day, month or year is unknown, but all three fields are not unknown. An incomplete date occurs when the exact date an event occurred or ended cannot be obtained from a subject. For many of the analyses, a complete date is necessary to determine if the event should be included in the analysis (i.e., if the event is treatment-emergent) or to establish the duration of an event. In such cases, incomplete dates will be imputed as follows.

For concomitant medications, the case report form permits the start date to have an unknown day and/or month.

6.3.6.1. Start Dates for Concomitant Medications

- For missing start day only – Day will be imputed as the first day of the month (i.e., 1) with the following exception: If the partial date falls in the same month and year as the treatment start date then the concomitant medication start date will be imputed as the treatment start date.
- For missing start day and month – Day and month will be imputed as the first day of the year (i.e., 1 January) with the following exception: If the partial date falls in the same year as the treatment start date then the concomitant medication start date will be imputed as the treatment start date.

6.3.6.2. Stop Dates for Concomitant Medications

- For missing stop day only – Day only will be imputed as the last day of the month (i.e., 28, 29, 30, or 31).
- For missing stop day and month – Day and month will be imputed as the last day of the year (i.e., 31 December).

For adverse events, the case report form permits the date to have an unknown day. If day is missing, then a question on the case report form asks whether the event started prior to the first dose.

6.3.6.3. Start Dates for Adverse Events where the event occurs prior to the first dose

- For missing start day only – Day will be imputed as the first day of the month (i.e., 1) with the following exception: If the partial date falls in the same month and year as the treatment start date then the adverse event start date will be imputed as the day prior to the treatment start date.

6.3.6.4. Start Dates for Adverse Events where the event is not prior to the first dose

- For missing start day only – If the partial date falls in the same month and year as the treatment start date then the adverse event start date will be imputed as the treatment start date. Otherwise, the day will be imputed as the first day of the month (i.e., 1) as long as the imputed date does not occur before the treatment start date.

6.3.6.5. Stop Dates for Adverse Events

- For missing stop day only – Day only will be imputed as the last day of the month (i.e., 28, 29, 30, or 31).

For study drug exposure, the case report form permits the date to have an unknown day. However, due to daily dosing, partial dates will not be imputed.

Any partial dates will be displayed in data listings without imputation of missing days and/or months (e.g., JAN2017, 2015).

6.4. TIMING OF ANALYSES

When all Group 2 randomized subjects have reached 24 weeks of study participation or discontinues from study early, and once all data have been cleaned and database frozen for analysis, the safety and efficacy analysis of GBT440-031 will be performed according to this SAP.

7. ANALYSIS POPULATIONS

7.1. Intent to Treat (ITT) Population

All subjects who were randomized in the study will be included in the ITT population. Subjects will be analyzed based upon the treatment group to which they were assigned at randomization. This is the primary population for efficacy analysis.

7.2. Modified Intent to Treat (mITT) Population

All subjects who are randomized to a treatment group and receive at least one dose of study medication will be included in the Modified Intent to Treat Population. Subjects will be analyzed based upon the treatment group to which they were assigned at randomization. Selected efficacy endpoints, e.g., Hb response rate, may be analyzed based on the mITT population as supportive analysis.

7.3. Safety Population

All subjects who receive at least one dose of study medication will be included in the Safety Population. Subjects will be analyzed based upon study treatment they received. This is the primary population for safety analyses.

8. STATISTICAL METHODS

Statistical programming and analyses will be performed using established statistical methods. Information related to blinding (and unblinding) during the conduct of the study is provided in [Section 6.2](#) and in Protocol Section 8.3. All statistical tests will be conducted at a two-sided significance (alpha) level of 0.05 unless otherwise stated.

The study data will be reported using tables, figures, and data listings. Descriptive statistical methods will be used to summarize the data from this study. Continuous variables will be descriptively summarized using number of subjects (n), mean, standard deviation (SD), coefficient of variation (CV%, as appropriate), median, minimum, maximum, inter-quartile range (IQR), and, geometric mean as appropriate. Categorical variables will be descriptively summarized by presenting the number (frequency) and percentage in each category. Kaplan-Meier or cumulative incidence curves will be used to present time to event or recurrent event data, as appropriate. Data for subjects who provide diary data but discontinue treatment and continue in the study will be included in the analysis. Hypothesis testing will be performed for the primary and select endpoints as specified in [Section 6.3.3](#).

Unless otherwise noted, data listings will be sorted by treatment group, subject number, and then, where applicable, by visit or assessment date within each subject number.

The statistical analyses will be conducted with the SAS[®] System version 9.4 or higher. All analyses will be subject to formal verification procedures. Specifically, results will be verified utilizing independent programming prior to issuance of the draft statistical analysis outputs. All documents will be verified by the lead statistician to ensure accuracy and consistency of analyses.

